The effect of Vigabatrin on Insulin Sensitivity

NCT04321395

Principal Investigator:

[name]
Washington University School of Medicine in St. Louis, Missouri

Version 7
December 15, 2022

SPECIFIC AIMS

Nonalcoholic fatty liver disease (NAFLD) is a common complication of obesity and is associated with hyperinsulinemia, multi-organ insulin resistance and an increased risk of developing type 2 diabetes (T2D). The hallmark feature of NAFLD is an increase in intrahepatic triglyceride (IHTG) content. Data from studies conducted in rodent models suggest increased IHTG content can cause insulin resistance through signaling by the hepatic vagal afferent nerve (HVAN). In rodent models of obesity and NAFLD, HVAN activity is reduced leading to impaired insulin sensitivity and glucose control. The reduction in HVAN activity is likely due to increased hepatic release of GABA, an inhibitory neurotransmitter, attributable to increased expression of GABA-Transaminase (GABA-T). In lean rodents GABA-T acts to break down high levels of GABA to produce succinate semialdehyde and glutamate, but in the livers of obese mice, the opposite reaction occurs with increased succinate semialdehyde and glutamate availability driving the GABA-T reaction toward GABA production, rather than breakdown. Pharmacological inhibition of GABA-T in obese mice by treatment with vigabatrin, an irreversible inhibitor of GABA-T that is approved by the FDA to treat seizure disorders, improves glucose tolerance and reduces hyperinsulinemia, hyperglycemia, and insulin resistance. It is not known if vigabatrin can also improve metabolic function in people.

The overall goals of this pilot study are to determine the potential effect of vigabatrin on insulin sensitivity, insulin secretion and glycemic control in people with obesity and NAFLD (IHTG content $\geq 5.6\%$). Accordingly, we will conduct a 3-week, single-arm trial to assess the effect size of treatment with vigabatrin on the following specific aims with the larger goal of determining whether a large, randomized controlled trial investigating the effect of vigabatrin is warranted:

Aim 1: Determine the effect of GABA-T inhibition on insulin sensitivity in people with NAFLD. We will perform hyperinsulinemic-euglycemic clamp procedures plus stable isotope tracer infusions to assess skeletal muscle insulin sensitivity before and after treatment.

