Summary: Nonalcoholic fatty liver disease is associated with insulin resistance, and is an important risk factor for the development of T2D and CVD. Studies conducted in mouse models have shown a mechanistic link between NAFLD and insulin resistance; obese animals with NAFLD have an increase in hepatic GABA which decreases HVAN activity which in turn induces insulin resistance. Use of vigabatrin, an FDA-approved drug for seizure disorders, lowers hepatic GABA release and improves glucose tolerance and insulin sensitivity. However, the effect of vigabatrin on glucose tolerance and insulin sensitivity in people with obesity and NAFLD is not known. Accordingly, the goal of this study is to conduct a pilot study to determine whether GABA-T inhibition may improve metabolic function in people with obesity and NAFLD and a larger, randomized controlled trial investigating the effect of vigabatrin is warranted.

[figure not shown]

Figure 3. NADH significantly higher in obese livers (A) GABA reduced with succinate dehydrogenase inhibitor (B)

APPROACH

Study Participants

A total of 6 adults (18-60 years old) with obesity (BMI 30.0-49.9 kg/m²), NAFLD (IHTG content \geq 5.6%), and insulin resistance (Homeostatic Model of Insulin Resistance (HOMA-IR) Score²⁹ $>$ 2.5), of all races and ethnic groups will be enrolled in this study.

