Vision testing will be repeated during the clamp visit (day 23). Vision and depression (Beck Depression Inventory-II³⁰) will be assessed approximately 6 months after participants initiated the drug.

Table 1. Schedule of tests performed

Assessment	SCREENING			BASELINE TESTING		WEEK 3 TESTING		STUDY COMPLETION
	Visit 1	Visit 2	Visit 3	Visit 1	Visit 2	Visit 1	Visit 2	
Informed Consent	X							
Anthropometrics								
Weight	X			X	X	X	X	X
Height	X							
Vital Signs								
Blood Pressure	X			X	X	X	X	X
Heart Rate (Pulse)	X			X	X	X	X	X
Respirations	X			X	X	X	X	X
Temperature	X			X	X	X	X	X
Medical Evaluation								
Medical History	X							
Physical Examination	X							X
12-Lead Electrocardiogram	X							
Depression Screening	X					X		X
Lab/Blood Work								
Urine pregnancy test (females only)	X	X	X	X	X	X	X	
Urine drug test	X	X	X	X	X	X	X	
PT/INR	X							
CBC/diff	X					X		
CMP	X					X		
Lipid panel	X					X		
HbA1C	X					X		
Body composition analysis								
Dual energy X-ray absorptiometry (DXA)				X				
Abdominal MRI			X			X		
Liver volume, TG content and stiffness by MRI/MRE			X			X		
Metabolic function								
Modified 3-hour oral glucose tolerance test (mOGTT)				X		X		
Hyperinsulinemic-euglycemic clamp (HEC)					X		X	
Vision Testing								
Peripheral Vision Tests			X				X	X

Statistical Analyses

Statistical Analysis: The effect size of vigabatrin treatment on insulin sensitivity during the HEC and insulin secretion assessed during the mOGTT will be determined by using Cohen's d tests. Using these effects sizes we used G*Power 3.1.9.2 to estimate the number of participants per group that would be required to detect an ~15% improvement in insulin sensitivity between placebo and vigabatrin groups with >90% power using two-sided tests at the $\alpha=0.05$ level if a randomized, controlled trial were to be conducted.

PROTECTION OF HUMAN SUBJECTS

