Human Subjects Involvement and Characteristics. A total of 6 men and women of all races and ethnic groups will be studied. Subjects will be screened carefully with a medical history and physical examination, and blood tests. Exclusion criteria will include: 1) previous bariatric surgery; 2) structured exercise ≥ 250 min per week (e.g., brisk walking); 3) unstable weight ($>4\%$ change during the last 2 months before entering the study); 4) significant organ system dysfunction (e.g., diabetes, severe pulmonary, kidney or cardiovascular disease); 5) cancer; 6) polycystic ovary syndrome; 7) major psychiatric illness (including suicidal ideation or previous suicide attempts); 8) conditions that render subject unable to complete all testing procedures (e.g., severe ambulatory impairments, limb amputations, or metal implants that interfere with imaging procedures; coagulation disorders); 9) regular use of tobacco products; 10) excessive consumption of alcohol (≥ 3 drinks/day for men and ≥ 2 drinks/day for women); 11) use of medications that are known to affect the study outcome measures or increase the risk of study procedures and that cannot be temporarily discontinued for this study; 12) pre-existing visual field deficits; or those at high risk of irreversible vision loss, including patients with retinopathy or glaucoma; 13) pregnant or lactating women; 14) conditions that render subject unable to complete all testing procedures (e.g. aversion to needles, metal implants that prevent magnetic resonance imaging); 15) persons who are unable or unwilling to follow the study protocol; 16) persons who are not able to grant voluntary informed consent; 17) patients at risk for severe anemia (hemoglobin less than 13.5 gram/100 ml in men or 12.0 grams/100 ml in women or hematocrit $< 39\%$ in men or $< 36\%$ in women); 18) patients with a heart failure or a history of lower limb edema; xxii) patients with mild or more severe renal insufficiency (CLcr < 80 mL/min/1.73m²); 19) patients with existing peripheral neuropathy; 20) and women who have active menstrual cycles but are not using birth control (acceptable contraception includes barrier/hormonal/IUD).

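### The only planned estimate is a Cohen's d from six before-after pairs, with no interval or small-sample correction; it cannot be relied on to judge or size a later trial at more than 90% power

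*Combined protocol and SAP*

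**What the plan says.** Specific Aims describes a "3-week, single-arm trial to assess the effect size of treatment with vigabatrin", "with the larger goal of determining whether a large, randomized controlled trial investigating the effect of vigabatrin is warranted". Study Participants fixes the size: "A total of 6 adults (18-60 years old) with obesity". Human Subjects Involvement and Characteristics gives the same number.

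The Statistical Analyses section is two sentences long. The first says that the effect on clamp insulin sensitivity and on insulin secretion in the glucose tolerance test "will be determined by using Cohen's d tests". The second begins "Using these effects sizes we used G*Power 3.1.9.2" and gives the aim as the number per group "required to detect an ~15% improvement in insulin sensitivity" "between placebo and vigabatrin groups with >90% power using two-sided tests" at alpha 0.05, should a randomised trial follow.

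The section gives no confidence interval, no test, no small-sample correction and no standardiser for d (SD of change, baseline SD or pooled SD). It also gives no SD, no value of d and no number per group. It names two possible drivers of the later sample size, the observed effect sizes and a fixed improvement of about 15%, without saying how they combine.

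**The concern.** The pilot has two products: a judgement on whether a randomised trial is warranted, and a sample size for it. Both rest on one point estimate from six pairs. At that size d has two weaknesses. It divides by an SD with few degrees of freedom, so on average it is too large. It is also so imprecise that the point estimate alone says little. Reported without an interval, a d that convention calls large could be compatible with no effect or with harm, and a trial sized from it could easily be underpowered.

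**Working it through.** **Inputs from the protocol.** n = 6 before-after pairs (Study Participants), so 5 df for the SD of within-person change; target about 15%, power 90%, two-sided alpha 0.05 (Statistical Analyses).

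**Assumptions, not in the documents.** d is standardised by the SD of paired change; data are normal; the later trial has 1:1 allocation and no dropout; the pilot's paired scale equals the later trial's between-group scale; true d lies between 0.5 and 1.5.

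**The plan's own figure.** The power of more than 90% can be neither reproduced nor refuted, because no n, SD or d is stated.

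**1. Bias of d.** J(5) = Γ(2.5) / (√2.5 × Γ(2)) = 1.329 / 1.581 = 0.841. The mean of d over its true value is 1/0.841 = 1.189, an overstatement of 19%. The distribution is skewed, and the simulated median overstatement is about 6%. With a pooled SD on 10 df, J = 0.923 and the mean overstatement is about 8%.

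**2. Precision.** Inverting the noncentral t, with t = d√6:

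| Observed d | 95% CI |
|---|---|
| 0.5 | -0.38 to 1.33 |
| 0.8 | -0.16 to 1.71 |
| 1.0 | -0.03 to 1.97 |

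The half-width of the interval for the mean change is t(0.975, 5)/√6 = 2.571/2.449 = 1.05 SDs of change. An observed mean change of 15% therefore excludes zero only if that SD is below 15/1.05 = 14.3 percentage points.

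**3. What this does to the sample size.** For a two-sample t test at 90% power, d = 0.8 needs 34 per group. The corrected value, 0.8 × 0.841 = 0.67, needs 48. The upper limit, 1.71, needs 9. The lower limit is negative and gives no sample size.

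**4. Power actually achieved.** With n per group = 2 × (3.2415/d̂)², where 3.2415 = 1.960 + 1.282, the true power is Φ(3.2415 × δ/d̂ − 1.960). The two readings of the plan were simulated.

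- *Sizing on the observed d* (estimates of 0.05 or less dropped):

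| True d | Mean power | Pilots giving power below 90% |
|---|---|---|
| 0.5 | 68% | 60% |
| 0.8 | 75% | 55% |
| 1.0 | 76% | 55% |
| 1.5 | 78% | 56% |

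- *Sizing on a fixed 15% with the pilot SD*: power is Φ(3.2415 × s/σ − 1.960), which is below 90% whenever s < σ. That probability is P(χ²₅ < 5) = 58%. Mean power is 78%, median power about 86%, and 41% of pilots give less than 80%.

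These results use n before rounding. Rounding n up to whole participants gives mean power of 69-80% and 79-81% for the two readings, with 54-60% and 56-58% of pilots below 90%.

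**5. Bias or sampling error?** On the fixed-15% reading, n is proportional to s² and the mean of s² is σ². Mean n is therefore right and median n is about 13% low; the power is lost through the spread of s². On the observed-d reading, applying Hedges' correction raises mean power only to about 76-87%, and 38-51% of pilots still fall below 90%. Correcting the bias alone does not solve the problem.

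**6. A conservative SD.** The one-sided 80% upper limit is √(5/2.343) = 1.46 times the observed SD, and it multiplies n by 1.46² = 2.13. Power is then at least 90% in 80% of pilots, which follows from how the limit is defined; mean power is 93%.

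**The case against.** This is a declared pilot whose purpose is to estimate an effect size. The randomised trial is conditional, and nothing in the pilot's conduct or safety depends on the point. That is fair. It limits the importance of the point, but the estimate and the sizing are exactly what the pilot is meant to deliver.

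Three stronger readings are tempting, and the documents do not support them.

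- A reader might infer that the later trial does not have its stated power. With no n, SD or d given, this cannot be shown. The figure is a design target, and on the calculation above some 40-45% of pilots would give at least 90% power.
- A reader might square the factor, 0.841² = 0.707, and infer that n is 29% too small. That evaluates n at the average d. On the fixed-15% reading mean n is unbiased.
- A reader might insert the average overstatement, Φ(3.2415 × 0.841 − 1.960) = 78%, and blame bias for the loss of power. Mean power on the fixed-15% reading happens to be similar, but it comes from sampling error.

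The 19% also depends on an unstated standardiser and is a mean drawn up by a long tail. The absence of a correction is read from the plan's silence, although Cohen's d in its plain form has none. Finally, treating a paired d as a between-group d is a strong assumption. At an assumed pre-post correlation of 0.7 or 0.9, the factor 1/√(2(1 − ρ)) makes the paired d 1.29 or 2.24 times a d based on the raw SD, which is a larger discrepancy than the 19%.

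**Conclusion.** The point holds in a limited form. A d or SD from six pairs, plugged in without an interval, cannot be relied on to support the decision about a randomised trial or to deliver more than 90% power. On the stated assumptions, about 55-60% of pilots would produce a trial below 90% power, and mean power is about 68-78%. Imprecision does most of the damage. The bias of 19% on average (median about 6%; about 8% on average with 10 df) is real but secondary, and it depends on the standardiser. Whether any particular later trial would be underpowered cannot be determined from the documents. The change is worth making because it is cheap and improves the pilot's main output.

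**What to change.** In Statistical Analyses:

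- State the standardiser used for d.
- Report Hedges' g (d × 0.841 for paired change at n = 6) with its 95% confidence interval.
- Report the mean within-person percent change in clamp insulin sensitivity with its SD and 95% confidence interval beside the 15% target. Call an interval that contains both 0 and 15% inconclusive.
- Size the later trial on the 15% difference with a conservative SD, for example an upper confidence limit. The one-sided 80% limit (1.46 times the observed SD) is one reasonable choice, not a requirement. Alternatively, show n per group over the confidence range of the SD. For illustration, assumed SDs of 10, 15, 20, 30 and 40 percentage points give 11, 23, 39, 86 and 151 per group for a 15% difference.

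The cost is some SAP wording and a few lines of analysis, with no new participants or data. The quoted effect size will be smaller and the projected trial larger, by a factor of about 2.1 in n if the 80% limit is used.

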infection. The total amount of blood collected during the full set of research procedures will be ~500 mL including all screening, baseline, post-treatment and medical monitoring visits . If a participant develops a health problem or potential health problem, the PI/study physician and, if necessary a medical consultant who is not part of the research team, will decide whether the participant should be continued in the study, and/or what further steps regarding medical evaluation/treatment should be performed. The CTRU and hospital facilities used for the study are equipped with defibrillators and all appropriate emergency medications. Should the need for medical treatment arise, the PI/study physician will arrange for medical evaluation at the Washington University School of Medicine, which provides all the resources of a large teaching hospital for subject evaluation and treatment. The subject and the primary care physicians will be made aware of any abnormal findings while participating in the study. The participants will be given the phone numbers of the members of the research team (including an emergency phone number) and told to call a member of the research team immediately if they develop any unusual signs or symptoms. Subjects will be screened for depressive symptoms before starting treatment, while on treatment and at study completion. If the subject reports significant increase in depression or thoughts of suicidal ideation, the subject will be removed from the study and immediately be sent for psychiatric evaluation. Vision testing will be completed in all subjects at baseline, after a week at the maximum dose and then 6 months after drug initiation. If vision changes are noted, subjects will be referred for further testing and evaluation by an ophthalmologist.

Potential benefits of the research to the participants

Potential benefits to the participants include obtaining information regarding their body composition and a medical examination. Participants' basal measures of glucose homeostasis may improve with this treatment. These results could support the findings from studies conducted in rodent models and lead to a new approach for treating metabolic abnormalities in people.

Importance of the knowledge to be gained

The information gained from this work has important public health implications in the potential of development of a new drug for treatment or prevention of NAFLD.

Data and safety monitoring plan

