Data from the study will be monitored on a continual basis by the PI. All serious adverse events (SAEs), adverse events (AEs), and laboratory values will be reviewed by the PI on an ongoing basis. The PI will be responsible for annual reports to Washington University School of Medicine's IRB and for reporting any adverse events to the IRB.

The IRB at Washington University School of Medicine defines unanticipated problems (adverse events) as involving risks to participants or others which are: 1) unexpected (in terms of nature, severity, or frequency) given (a) the research procedures that are described in the study-related documents, such as the IRB-approved research study and informed consent document; and (b) the characteristics of the subject population being studied; and 2) are related or possibly related to participation in the research; and 3) suggest that the research places participants or others at a greater risk of harm (including physical, psychological, economic, or social harm) than was previously known or recognized.

Adverse events will include vision loss, suicidal behavior, anemia, peripheral neuropathy, edema, ear disorders: deafness, gastrointestinal disorders, hepatobiliary disorders (cholestasis), nervous system disorders (dystonia, encephalopathy, hypertonia, hypotonia, muscle spasticity, myoclonus, optic neuritis), psychiatric disorders (acute psychosis, apathy, delirium, hypomania, neonatal agitation, psychotic disorders), respiratory disorders (laryngeal edema, pulmonary embolism, respiratory failure, stridor skin), and/or subcutaneous tissue disorders (angioedema, maculo-papular rash, pruritus, Stevens-Johnson syndrome (SJS), toxic epidermal necrolysis (TEN))

Adverse Event Reporting: All AEs will be graded according to the following scale:

- 0 = No adverse events or within normal limits
- 1 = Mild; did not require treatment
- 2 = Moderate; resolved without treatment
- 3 = Severe; required professional medical attention
- 4 = Life-threatening or disabling

5 = Death

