The PI will review AEs and notify the IRB of any changes needed to the protocol. The IRB will be notified within 24 hours of any SAE (grade 4 or 5) occurring at this site via their online system for reporting SAEs, and additional information will be forwarded to the IRB as it becomes available. AE's (grades 2-3) will be reported by the PI to the IRB within 10 working days. Mild AE's (grade 1) will be reported at the annual continuing review. In addition, all laboratory values outside of the normal range will be discussed with the study participant, and appropriate arrangements will be made for treatment, if necessary. The annual summary of all adverse events and any audit reports will be sent to the IRB at the time of continuing review.

If the data received during the course of the study on a study participant indicate they he or she may benefit from (other) medical intervention, then the appropriate recommendation(s) and/or consultation(s) will be made.

A Data and Safety Monitoring Board, chaired by [name] MD (Professor of Medicine), and including [name] (Associate Professor of Medicine) will meet every 12 months with the PI, Co-Investigators, and the study research coordinator, to review study data, discuss any safety issues, and ensure compliance with the protocol.

Study Withdrawal/Discontinuation

Participants are free to withdraw at any time. Female participants who become pregnant will be removed from the study. If the participant's doctor decides that staying in the study places the participant at risk, she/he will be withdrawn. Any condition deemed by the study personnel to interfere with the participant's ability to complete the study will be cause for withdrawal. Subjects will be removed from study if they no longer meet the study criteria, if an SAE occurs, if they do not show up to study visits, or if the study is terminated.

Subjects that are removed or withdraw from the study will initiate the drug step-down protocol by decreasing their drug dose by 1000 mg for one week prior to stopping the drug completely.

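### AE grades 1 and 2 overlap and self-treated events fit no grade, so the plan does not fix when the IRB hears of an event

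*Combined protocol and SAP*

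**What the plan says.** Under Adverse Event Reporting, the Data and safety monitoring plan applies a single 0-to-5 scale: "All AEs will be graded according to the following scale". The lines at issue are:

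- "1 = Mild; did not require treatment"
- "2 = Moderate; resolved without treatment"
- "3 = Severe; required professional medical attention"

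Grade 0 is the absence of an event or a normal result, grade 4 is "4 = Life-threatening or disabling", and grade 5 is death. Each of grades 1 to 3 pairs a severity word with a clause about treatment or care. The severity words are not defined, and nothing says which part governs when word and clause disagree.

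The same section ties IRB reporting to the grade: 24 hours for grades 4 and 5, and 10 working days for grades 2 and 3. For the lowest grade, "Mild AE's (grade 1) will be reported at the annual continuing review".

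Adequacy of protection against risks adds a referral rule with no size threshold: "If vision changes are noted, subjects will be referred for further testing and evaluation by an ophthalmologist". Vision loss is first in the plan's list of adverse events, so the scale applies to it.

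**The concern.** A grading scale that drives reporting deadlines has to give each event one grade. Here the clauses for grades 1 and 2 describe nearly the same situation (no treatment), and nothing between grade 2 and grade 3 covers treatment without professional care. Two people applying the text in good faith could grade one event differently, or find no line that fits.

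At stake is the time to IRB notification and the consistency of the severity record. Dosing lasts 30 days and the last visit is about 6 months after the drug is started. A report held for the annual review can therefore arrive after the participant has finished dosing, and possibly after the last visit.

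**Working it through.** The plan states no figure on this point, so there is none to reproduce. The check matches event types to the clauses for grades 1 to 3 and then reads off the reporting time for each match.

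Inputs: the grade lines and reporting times (Data and safety monitoring plan), and the vision referral rule (Adequacy of protection against risks).

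| Event | Grade 1 clause | Grade 2 clause | Grade 3 clause | Resulting IRB deadline |
|---|---|---|---|---|
| (a) Needs no treatment and resolves | met | met | not met | annual review or 10 working days |
| (b) Needs treatment, self-treated, no professional attention required | not met | not met | not met | none assigned |
| (c) Moderate, untreated, persists | met, but the word Mild does not fit | not met (not resolved) | not met | annual review if the clause governs; 10 working days if the word governs |
| (d) Vision change, referred, needs no treatment | met | met only if it resolves | met on a literal reading | annual review or 10 working days |
| (e) Disabling vision loss | – | – | – | grade 4: 24 hours |

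Notes on the rows:

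- **(a)** Only the undefined severity words separate the two matching grades.
- **(b)** This assumes that an event the participant treated did require treatment. If it is argued that the treatment was taken but not needed, the event returns to grade 1, and that argument would have to be made case by case. Grade 0 does not help, because an event occurred. Grades 4 and 5 do not apply to an event that is neither disabling, life-threatening nor fatal.
- **(c)** Tingling that continues untreated is an example; it is among the side effects listed under Potential Risks. No line fits both its intensity and its course.
- **(d)** The referral is for evaluation and may lead to no treatment, so the clauses for grades 1 and 3 can hold together.
- **(e)** This row is unambiguous and shows that the top of the scale works.

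Size of the gap: 10 working days is 2 calendar weeks on a five-day week. Annual review means a wait of up to about 12 months, depending on where the event falls in the review cycle.

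**The case against.** The strongest reply is that Mild, Moderate and Severe are themselves criteria, and an experienced investigator can use them to separate grades 1 and 2. The practical safeguards also do not wait for the grade. The PI reviews all events and laboratory values on an ongoing basis, participants are seen weekly while on drug, vision and psychiatric referrals do not depend on the grade, and every event enters the annual IRB summary. The 24-hour rule rests on grades 4 and 5, which the ambiguity does not reach. The longest delay applies only to events that end up called mild. Tightening the existing clauses and adding a line for self-treated events might be enough.

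Much of this stands. The harm is limited to reporting time and to the consistency of the record, and it would be wrong to say that the scale ignores severity: care-based clauses appear only in grades 1 to 3, and beside a severity word. But the words are undefined, and in rows (b) and (c) they conflict with the clauses attached to them. PI review does not say which grade or deadline applies. The Data and Safety Monitoring Board is scheduled every 12 months, so it is no faster route.

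A reader might go further and infer that every referred vision change must be graded Severe. The text does not say so. Grade 3 is one literal reading, a referred change needing no treatment also meets the grade 1 clause, and disabling loss is grade 4. That reading would also prove too much: Potential Risks tells participants to contact their own physician and the study physician about any listed side effect, headache included, so nearly every event could become Severe. The grade of a referred vision change is undetermined.

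**Conclusion.** The point holds as a defect in the grading rule and in the reporting rule that depends on it. Followed as written, the plan gives two possible grades to an event that resolves untreated, no grade to a self-treated event that needed treatment, no fully fitting grade to a moderate untreated event that persists, and an undetermined grade to a referred vision change that needs no treatment. The deadline is then 10 working days, the annual review, or unassigned. This rests on the wording alone and, for self-treated events, on the assumption that treatment was required.

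Three further inferences are not supported:

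- **A rate of severe events.** One referred vision change among 6 participants would be 1/6 = 17%, but that supposes both the event and the contested grade 3 reading, and the plan specifies no adverse event rate analysis.
- **A claim that most common reactions cannot be graded.** The label summary under Potential Risks lists reactions without saying how they were treated, and untreated events that resolve can be graded, only not uniquely.
- **A distorted decision on a larger trial.** Specific Aims and Statistical Analyses base that decision on effect sizes for metabolic outcomes, not on adverse event grades.

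The number of events affected cannot be estimated from the documents. The change is worth making because it is cheap and concerns safety reporting. It does not touch the efficacy estimates.

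**What to change.** Reword grades 1 to 3 so that every non-serious event meets exactly one of them. One way is to grade by intensity and interference with usual activities: none or minimal for grade 1, some for grade 2, marked but not disabling for grade 3. Keep grades 4 and 5 and the present reporting times.

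Move the care information into separate fields on the adverse event form: treatment given (none, self-administered, professional), referral (and whether the protocol required it), and resolution (resolved or ongoing, with date). State that a referral required by the protocol does not by itself set the grade. Say also how findings on vision tests are graded, since a change without symptoms may not interfere with activities.

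The cost is an amendment to the protocol wording and the form. The small downside is that the investigator must judge intensity instead of reading the grade from the care received. No dose, visit or referral rule changes.
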